This study is a prospective observational study. This clinical study compared the treatment effect of 50% diluted AS eye drops 8 times a day, as compared to conventional PFAT 8 times a day plus 0.05 % COE 2 times a day in patients with severe DES based on ocular surface disease index (OSDI), Oxford scale, TBUT, schirmer's test score. OSDI score more than 40 and Schirmer's test without anesthesia below 10 mm / 5 minutes were accepted as severe DES in our study. Informed consent was obtained from each patient in the study. The Ercives University School of Medicine Institutional Review Board approved the study protocol, which adhered to the guidelines of the Declaration of Helsinki. The patients enrolled in the study all had dry eye whose schirmer's test scores were below 5mm/5 minute. The Schirmer's test I (without anaesthesia) was graded in millimetres after 5 min.(13) 18 patients had 50% diluted AS eye drops 8 times a day, the other 18 patients had conventional PFAT(polivynil alcohol- povidone) 8 times a day plus 0.05 % COE (Restasis; Allergan, Inc., Irvine, CA) 2 times a day. 36 patients (totally 72 eyes) with severe dry eye syndrome were refractory to conventional treatment (those that did not respond well to entire dry eye medications containing hydroxypropyl methylellulose, carboxyl methylcellulose, polyvinyl alcohol, polyethylene glycol-propylene glycol, sodium hyaluronate, mineral oil, dextran, and carbomer artificial tears with or without preservatives), had low TBUT (< 5 s) (5µL of fluorescein sodium 2% eye drops was used), low Schirmer's test I score without topical anesthesia ( basic+reflex secretion), positive corneal and conjunctival fluorescein staining (>grade 1 according to the OXFORD Scale) (3) and an OSDI score > 40 OSDI was a reliable and valid test for quantifying the severity of dry eye symptoms.(14) Patients with an active ocular infection or any other inflammation not associated with dry eye, a severe associated ocular allergy, eyelid or eyelash abnormality, current contact lens use, history of refractive surgery, associated glaucoma, and current use of any type of topical eye drops other than dry eye medications, any known graft-versus host disease, known severe anemia (hemoglobin<11

g/dL), and medically uncontrolled significant cerebrovascular and cardiovascular disease, pregnant and lactating patients were excluded.

After informed consent was obtained, 15 mL venous whole-blood samples were drawn once from each patient at the beginning of the study for AS preparation. We followed the methods of Celebi et al.(15) Serum drops were produced as a 50% formulation. After venosection blood in sterile container centrifuged at 4000 rpm for 10 minutes, serum was taken from the biochemistry blood tube and 50% formulation of AS was prepared in 50% concentration by mixing sterile isotonic 0.9% NaCl solution in the eye drop container. 50% diluted AS using patients were told to keep the AS drops at 4 °C in refrigerator. All the patients were instructed to use 8 drops a day time (1 drop every 2 h in awaken times) in each eye. The designation of the patient whether to use AS 8\*1 or conventional PFAT 8\*1 plus COE 2\*1 was determined randomly. The beneficial effects of two therapeutic regimes were explained and the patient chose the treatment. The study data were collected and statistical analyzes were done after the enough number of participants were reached. OSDI, TBUT, Schirmer's test I, and OXFORD scales were administered before and after first month. Statistical analyses were performed using SPSS version 15.0 for Windows Evaluation Version release (SPSS, Inc., Chicago, IL). Descriptive statistics were presented as mean  $\pm$  SD for the variables (OSDI score, Schirmer's Test I and TBUT), and as median with interquartile range (IQR) for the ordinal variable (OXFORD Scale). All the variables were normally distributed except Oxford scales data (Kolmogorov-Smirnov and Shapiro-Wilk tests). Student's paired samples t-test and independent samples Student's t-test were used to compare data. The Wilcoxon signed-rank test was used to compare the change in OXFORD scale scores. The Mann-Whitney U test was used to compare OXFORD scale scores between AS and PFAT+COE. All analyses were performed with a power of 80 % and 95 % CI. The level of statistical significance was set at p<0.05.

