Mean (SD) OSDI Score	Pre		Post	
AS	74.69		27.72	
PFAT+COE	79.70		37.30	
P value				
Between pre-post*	p<0.0001			
Between AS- PFAT+COE**	p=0.197 p=0.199		p=0.004 p=0.006	
*Student's paired samples t-test ** Independent samples Student's t-test				
Mean TBUT	Right eyes	Left eyes	Right eyes	Left eyes
AS	4.38	4.44	5.50	5.94
PFAT+ COE	3.83	4.11	7.11	6.88
P value				
Between pre-post*	p<0.001(right eyes) p<0.001(left eyes)			
Between AS- PFAT+COE**	p=0.121	p=0.345	p=0.04 p=0.034	
*Student's paired samples t-test ** Independent samples Student's t-test				
Median with interquartile range (IQR) OXFORD				
AS	2(9)		1(18)	
PFAT+COE	2(7)		1(14)	
P value				
Between pre-post*	p<0.0001			
Between AS- PFAT+COE**	p=0.366		p=0.296	
*Wilcoxon signed-rank test **Mann-Whitney U test				
Mean Schirmer's test Result	Right eyes	Left eyes	Right eyes	Left eyes
AS	6.77	5.94	8.83	9.55
PFAT+COE	6.33	6.33	18	18.83
P value				
Between pre-post*	p<0.0001(right)		p<0.0001(left)	
Between AS- PFAT+COE**	p=0.620	p=0.593	p<0.0001	p<0.0001
*Student's paired samples t-test ** Independent samples Student's t-test

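### The Protocol says allocation was random and, in the next sentence, that the patient chose; the unadjusted between-arm tests support a treatment effect by design only in the first case

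*Protocol*

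**What the plan says.** The Protocol's procedures and statistics paragraph says, across two consecutive sentences, that each patient's assignment to AS or PFAT+COE "was determined randomly. The beneficial effects of two therapeutic regimes were explained and the patient chose the treatment".

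The Protocol's opening paragraph labels the design: "This study is a prospective observational study". It then sets a comparative aim: "This clinical study compared the treatment effect of 50% diluted AS eye drops 8 times a day", against PFAT plus COE. It gives equal arms: "18 patients had 50% diluted AS eye drops 8 times a day, the other 18 patients had conventional PFAT" plus COE.

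For the continuous outcomes, "Student's paired samples t-test and independent samples Student's t-test were used to compare data". Between-arm Oxford grades are compared by a Mann-Whitney test. No covariate adjustment is specified. The SAP's results tables give between-arm p-values before and after treatment (for baseline OSDI, "p=0.197 p=0.199"). They contain no adjusted comparison and no between-arm test of change.

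**The concern.** One patient's arm cannot be set both by chance and by preference. The documents describe no scheme in which both could be true, such as randomisation alongside a preference cohort. They give no sequence generation and no concealment.

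The allocation method decides what the between-arm tests mean. A t-test or Mann-Whitney test validly compares the two observed groups either way. Random allocation is what would allow the difference to be read as an effect of treatment. If patients chose after hearing about the benefits of each regimen, the groups are self-selected. Preference, severity or expectation could then contribute to the difference, and OSDI is a symptom score. A reader who relies on the word random would draw a causal conclusion that a patient-choice design cannot support.

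**Working it through.** **1. The statements side by side**

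| Place | Statement | Fits random allocation? | Fits patient choice? |
|---|---|---|---|
| Protocol, procedures and statistics paragraph | Assignment was random | Yes | No |
| Same paragraph, next sentence | Patient chose | No | Yes |
| Protocol, opening paragraph | Observational study | No | Yes |
| Protocol, opening paragraph | Aim is to compare treatment effect | Yes | Only with further assumptions |
| Protocol, opening paragraph | 18 and 18 patients | Possible | Possible |

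The equal split does not decide the matter. Independent 50:50 assignment gives exactly 18/18 with probability C(36,18)/2^36 = 0.13, and blocking or enrolling to a quota would also give it.

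**2. OSDI gaps from the SAP means (PFAT+COE minus AS)**

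- Before: 79.70 − 74.69 = 5.01
- After: 37.30 − 27.72 = 9.58
- Difference in change: 9.58 − 5.01 = 4.57

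**3. Implied SDs**

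The text available here shows no SDs, so I back-calculated them, assuming a two-sided pooled t-test with 18 per arm and 34 df: SD = gap / (t × √(2/18)), where √(2/18) = 1/3. The SAP prints two OSDI p-values at each time point, so I used both.

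- Before: p=0.197 gives t = 1.316, SE = 3.81, SD = 11.42 (p=0.199: SD = 11.47).
- After: p=0.004 gives t = 3.088, SE = 3.10, SD = 9.31 (p=0.006: SD = 9.81).

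95% CI for the baseline gap: 5.01 ± 2.032 × 3.81, or about −2.7 to 12.8. In SD units the gap is 5.01/11.42 = 0.44. With 18 per arm, a baseline t-test has about 25% power for 0.44 SD (noncentrality 0.44 × √9 = 1.32). The non-significant baseline tests show neither balance nor imbalance.

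**4. OSDI gap adjusted for baseline (ANCOVA approximation)**

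The within-arm pre-post correlation r is not in the documents and is assumed.

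- Adjusted gap = 9.58 − r × (SDpost/SDpre) × 5.01
- SE² = [34 × SDpost² × (1 − r²)/33] × [2/18 + 5.01²/(34 × SDpre²)], with 33 df
- Change-score SD = √(SDpre² + SDpost² − 2 × r × SDpre × SDpost), with 34 df

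Worked case at r = 0.5: 9.58 − 0.5 × (9.31/11.42) × 5.01 = 7.54, SE 2.80, p = 0.011.

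| r | Adjusted gap (p), first p-values | Adjusted gap (p), second p-values | Change-score p for the 4.57 gap, first p-values |
|---|---|---|---|
| 0 | 9.6 (0.006) | 9.6 (0.008) | 0.36 |
| 0.5 | 7.5 (0.011) | 7.4 (0.017) | 0.20 |
| 0.9 | 5.9 (0.0002) | 5.7 (0.0005) | 0.011 |

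**5. Other outcomes (PFAT+COE minus AS)**

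| Outcome | Gap after | Difference in change |
|---|---|---|
| TBUT right, s | 7.11 − 5.50 = 1.61 | (7.11 − 3.83) − (5.50 − 4.38) = 2.16 |
| TBUT left, s | 6.88 − 5.94 = 0.94 | (6.88 − 4.11) − (5.94 − 4.44) = 1.27 |
| Schirmer right, mm | 18 − 8.83 = 9.17 | (18 − 6.33) − (8.83 − 6.77) = 9.61 |
| Schirmer left, mm | 18.83 − 9.55 = 9.28 | (18.83 − 6.33) − (9.55 − 5.94) = 8.89 |

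For TBUT the baseline gap runs against the final gap, so it cannot explain it. Schirmer hardly moves. Oxford shows no between-arm difference after treatment (p=0.296).

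**The case against.** The contradiction itself is not open to dispute. The best case against giving it weight has four parts.

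- **The figures say nothing about how patients were allocated.** The post-treatment and change gaps for OSDI differ by exactly the baseline gap under either rule, and a gap of 5.01 with p=0.197 is compatible with chance in a randomised study of 36. This stands: the factor of about two is not evidence of self-selection. Its relevance is narrower. Under random allocation both contrasts estimate the same effect in expectation; under choice they need not.
- **Adjustment does not overturn the OSDI result.** This also stands. What remains is unmeasured difference, which none of these figures measures. The 95% CI for the post-treatment OSDI gap has a lower limit of 9.58 − 2.032 × 3.10 ≈ 3.3 points (2.9 with p=0.006). A bias smaller than the observed baseline gap would bring that limit to zero.
- **The implied SDs are fragile.** The two printed OSDI p-values are unexplained and could, for example, be equal- and unequal-variance versions. The adjusted figures are therefore illustrations only.
- **An unadjusted comparison can be unbiased without randomisation if the groups happen to be comparable.** True, but nothing in the documents shows that, and 18 per arm cannot.

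The observational label makes the randomness statement the odd one out, but it does not prove which procedure was followed. The fix therefore has to cover both cases.

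**Conclusion.** The concern holds. The Protocol states two incompatible allocation rules, and which one is true decides whether the study is a randomised comparison or a comparison of self-selected groups. Selection bias is not shown; under patient choice it cannot be excluded.

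For OSDI, the contrast runs from 9.58 points (post-treatment) to 4.57 (change), with a baseline-adjusted value of roughly 5.7 to 9.6 and p below 0.05 at each correlation tried. Those adjusted values rest on pooled t-tests with 18 per arm, SDs recovered from rounded p-values, and assumed correlations of 0 to 0.9. The contradiction depends on none of these. It must be corrected because it changes what the study can conclude.

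**What to change.** State the one allocation method actually used, and make both Protocol paragraphs agree with it.

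- **If patients chose:** delete the statement that assignment was random and label the study non-randomised. Report between-arm comparisons adjusted for the baseline value already collected: ANCOVA for OSDI, TBUT and Schirmer, and an ordinal model with baseline grade for Oxford. Label these post hoc, since results are already printed. Word conclusions as associations, and say that adjustment does not remove unmeasured preference.
- **If a random list was used:** delete the patient-choice sentence and the observational label, describe how the list was generated and applied, and analyse by assigned arm.

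The cost is wording and, if patients chose, one re-analysis of existing data. No new data are needed. If patients chose, the price is a weaker causal claim.

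### The arms are compared on raw month-1 values with no baseline adjustment, although AS started 5.01 OSDI points better; ANCOVA would plausibly shrink the 9.58-point OSDI difference by 9-36% without changing its verdict

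*Protocol*

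**What the plan says.** The statistical sentences that close the Protocol give the methods for the three continuous outcomes: "Student's paired samples t-test and independent samples Student's t-test were used to compare data". For the ordinal outcome, "The Mann-Whitney U test was used to compare OXFORD scale scores between AS and PFAT+COE". Neither document mentions a baseline covariate or a between-arm test of change.

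The SAP tables show how this was applied. For OSDI, the between-arm row has "p=0.197 p=0.199" under the baseline column and "p=0.004 p=0.006" under the month-1 column. The arms are thus compared on raw values at each time separately. TBUT and Schirmer are handled the same way, with separate results for right and left eyes.

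The baseline data exist: OSDI, TBUT, Schirmer and "OXFORD scales were administered before and after first month".

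On allocation, the Protocol opens with "This study is a prospective observational study". It later says that assignment "was determined randomly", and in the next sentence: "The beneficial effects of two therapeutic regimes were explained and the patient chose the treatment".

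**The concern.** If the baseline value predicts the month-1 value, a raw month-1 contrast carries part of any baseline gap. Here the gaps are not trivial. AS started 5.01 points better on OSDI, more than half the month-1 difference of 9.58. It also started 0.55 s (right) and 0.33 s (left) better on TBUT. A baseline p of 0.197 with 18 patients per arm does not show balance.

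What the carried-over part means depends on allocation. If assignment was random, the raw contrast is unbiased over repeated trials, and the problem is conditional bias from the imbalance actually observed. If patients chose, it is confounding by baseline severity.

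Both OSDI and TBUT gaps flatter AS: the raw analysis probably overstates its OSDI advantage and understates the TBUT advantage of PFAT+COE. The two distortions therefore do not cancel when the regimens are weighed against each other.

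A secondary point is that separate right-eye and left-eye tests give two answers per outcome where one is wanted.

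**Working it through.** **Inputs.** There are 18 patients per arm (Protocol). Means and between-arm p-values come from the SAP tables. No SD is readable there, so the printed p-values cannot be reproduced independently and were inverted instead. The within-arm correlation r between baseline and month 1 is not given; 0.2 to 0.8 is an assumption. Tests are taken as two-sided.

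**Raw OSDI differences.** Baseline: d0 = 79.70 - 74.69 = 5.01. Month 1: d1 = 37.30 - 27.72 = 9.58.

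**Implied SDs.** SD = d / (t × √(2/18)), with t on 34 df.
- First p-values (0.197, 0.004): t = 1.316 and 3.088, so SD0 = 5.01/(1.316 × 0.3333) = 11.42 and SD1 = 9.58/(3.088 × 0.3333) = 9.31.
- Second p-values (0.199, 0.006): SD0 = 11.47 and SD1 = 9.81.

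The paired p-values are unlabelled and may be two versions of one t-test, so the second set is not an independent sensitivity case.

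**ANCOVA.** Slope b = r × SD1/SD0. Adjusted difference = d1 - b × d0. SE² = SD1² × (1 - r²) × (34/33) × [2/18 + d0²/(34 × SD0²)], with 33 df.

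Example (first set, r = 0.5): b = 0.5 × 0.815 = 0.4075, and the adjusted difference is 9.58 - 0.4075 × 5.01 = 7.54. SE² = 86.64 × 0.75 × 1.0303 × (0.1111 + 0.0057) = 7.82, so SE = 2.80, t = 2.70 and p = 0.011.

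| r | First set: difference (reduction), p | Second set: difference (reduction), p |
|---|---|---|
| 0.2 | 8.76 (8.5%), 0.009 | 8.72 (8.9%), 0.013 |
| 0.5 | 7.54 (21.3%), 0.011 | 7.44 (22.3%), 0.017 |
| 0.8 | 6.31 (34.1%), 0.003 | 6.15 (35.8%), 0.005 |

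The slope cannot exceed SD1/SD0 (0.81 to 0.86), so even at r = 1 the reduction is at most about 43-45%.

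**OSDI precision (first set).** The unadjusted 95% CI is 12.6 points wide. Adjusted widths are 12.9, 11.4 (1.85 to 13.23) and 7.9 (2.37 to 10.25) at r = 0.2, 0.5 and 0.8. Precision improves only above r of about 0.28.

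**TBUT.** The month-1 p-values for the two eyes share one cell. Read in order, the implied SDs are 1.04 and 2.26 s (right) and 1.03 and 1.28 s (left). The baseline gap runs against the month-1 gap, so adjustment enlarges the difference favouring PFAT+COE.

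| r | Right eye (raw 1.61 s), p | Left eye (raw 0.94 s), p |
|---|---|---|
| 0.2 | 1.85, 0.023 | 1.02, 0.023 |
| 0.5 | 2.21, 0.003 | 1.14, 0.005 |
| 0.8 | 2.57, <0.001 | 1.27, <0.001 |

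With the p-values swapped, the results are 1.84, 2.19, 2.54 (right) and 1.02, 1.15, 1.28 (left), and the largest p is 0.027. Outside the assumed range, at r = 0, right-eye ANCOVA (p-values in order) gives p = 0.0505, because a degree of freedom is lost and baseline is associated with arm.

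**Schirmer.** A month-1 p below 0.0001 gives only upper bounds on the SD (6.25 mm right, 6.32 mm left). The shifts at r = 0.8 are therefore maxima: right from 9.17 to at most 10.00 mm, left from 9.28 to no less than 8.37 mm, about 10% at most.

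**Comparison of change, for contrast.** OSDI fell by 74.69 - 27.72 = 46.97 on AS and by 79.70 - 37.30 = 42.40 on PFAT+COE, a difference of 4.57. With the SDs above, p is 0.31-0.32 at r = 0.2, 0.20-0.21 at r = 0.5 and 0.054-0.055 at r = 0.8.

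**The case against.** The strongest objection is that an unchanged verdict is a statement about ANCOVA only. The comparison of OSDI change is not below 0.05 anywhere in the assumed range, and if patients chose their arm, the two approaches can legitimately disagree. This stands as a limit on the wording. It does not weaken the point: if the OSDI conclusion depends on how baseline is handled, the plan must say how it is handled.

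Second, the size rests on an assumed correlation and inferred SDs. Entry limits on OSDI, TBUT and Schirmer narrow the baseline range and would tend to lower r, so the 0.8 end may be generous. The 36% end comes from the second p-value set. If 0.006 is an unequal-variance version of the same test, inverting it on 34 df is wrong and only the first set applies: 8.5-34%, with unequal variances that make the common-SD intervals less secure. The range is illustrative, but 34% against 36% is immaterial.

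Third, the contradictory account of allocation is the more serious defect, and neither document actually claims balance from the baseline p-values. Both are fair. The advice on baseline tests is a caution, and adjustment does not repair allocation by choice.

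Fourth, results already exist, so a change now is post hoc. That calls for a label; it is no reason to leave the baseline data unused.

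**Conclusion.** The point holds, and the analysis should be changed. The between-arm comparisons ignore baseline values that were collected for every outcome, in a study where AS started better on OSDI and TBUT and allocation is described in contradictory ways.

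Under an assumed correlation of 0.2 to 0.8, ANCOVA makes the OSDI advantage for AS 9-36% smaller and the TBUT advantage for PFAT+COE roughly 9-60% larger, depending on eye and correlation. Schirmer moves little. ANCOVA reverses no direction or significance verdict for OSDI or TBUT in that range, so what is at stake is the size of the reported effects. Confidence is medium, because the correlation is assumed, the SDs are back-calculated, and the TBUT figures depend on reading a shared cell. With truly random allocation the raw t-test remains valid over repeated trials. With patient choice, adjustment removes only the part due to the measured baseline value.

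**What to change.** - For OSDI, TBUT and Schirmer, make the between-arm analysis an ANCOVA of the month-1 value on arm and baseline value. Report the adjusted difference with its 95% CI.
- For TBUT and Schirmer, use the mean of both eyes, or a two-eye model with a patient random intercept, to give one estimate per outcome.
- For Oxford, use a rank-based or ordinal analysis adjusted for baseline.
- Do not treat baseline significance tests as evidence of balance.
- State how patients were allocated and, if they chose, that baseline adjustment does not remove other confounding.
- Since results are already tabulated, label the adjusted analysis post hoc, keep the unadjusted tests beside it, and show the OSDI comparison of change.

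The cost is analysis wording and a few lines of code, with no new data. The reported OSDI advantage for AS would probably be smaller and the TBUT advantage for PFAT+COE larger. If the pre-post correlation is below about 0.28, the OSDI interval would be slightly wider than the unadjusted one.

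### Four outcomes with no primary and no multiplicity rule, eye-by-eye tests of a per-patient treatment, and between-arm tests that leave out the baseline already measured

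*Protocol*

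**What the plan says.** The Protocol's design paragraph compares the two regimens "based on ocular surface disease index (OSDI), Oxford scale, TBUT, schirmer's test score" and puts these four outcomes in no order of importance. Its statistics text sets one threshold for everything: "The level of statistical significance was set at p<0.05". Neither document contains a primary outcome, a testing order or a multiplicity adjustment.

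Treatment is given per patient to both eyes: "1 drop every 2 h in awaken times) in each eye". Every outcome was measured twice: "OSDI, TBUT, Schirmer's test I, and OXFORD scales were administered before and after first month". For the continuous outcomes the method is described only as "Student's paired samples t-test and independent samples Student's t-test were used to compare data". Oxford has a Wilcoxon signed-rank test for change within arms and a Mann-Whitney test between arms.

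The SAP is a results table with separate pre and post columns. Its between-arm tests are made at each time point on its own. TBUT and Schirmer are tested separately for right and left eyes. OSDI has one mean per arm but two between-arm p-values at each time: "p=0.197 p=0.199" before treatment and "p=0.004 p=0.006" after. The pairs are not explained.

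**The concern.** Several tests each carry the full 5% error, and nothing says which of them decides. Testing each eye separately counts one treated patient twice within an outcome and adds two tests.

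This matters because the outcomes disagree. Post-treatment OSDI favours autologous serum (AS). Schirmer and TBUT favour artificial tears plus cyclosporine (PFAT+COE). Oxford does not differ. With no primary outcome, a reader could call either regimen better by choosing the outcome.

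The between-arm tests also leave out baseline. PFAT+COE started with higher OSDI and lower TBUT, so its arm looked worse on both before treatment. Ignoring this enlarges the apparent OSDI advantage of AS and shrinks the apparent TBUT advantage of PFAT+COE.

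**Working it through.** **The plan's own figure.** The Protocol gives 80% power for all analyses but ties it to no outcome, difference or SD, so it cannot be reproduced. With 18 per arm, a two-sided 5% t-test has 80% power for a difference of 0.96 SD.

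**Number of tests.** OSDI 1 + TBUT 2 + Oxford 1 + Schirmer 2 = 6 post-treatment between-arm tests. Seven p-values are printed because OSDI has two.

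**Error rate if no outcome differs.** Six independent tests: 1 − 0.95^6 = 0.265. All seven printed p-values, if independent: 1 − 0.95^7 = 0.302. Simulating six tests with assumed correlations of 0.5 to 0.9 between eyes and 0 to 0.3 between outcomes gives about 21% to 25%.

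**Holm on the printed p-values** (SAP table, post-treatment, six tests, 0.0001 used for p<0.0001):

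| Test | p | Multiplier | Holm p |
|---|---|---|---|
| Schirmer, two eyes | <0.0001 each | 6, 5 | ≤0.0006 |
| OSDI | 0.004 (0.006) | 4 | 0.016 (0.024) |
| TBUT left | 0.034 | 3 | 0.102 |
| TBUT right | 0.04 | 2 | 0.102 (raised to the value above) |
| Oxford | 0.296 | 1 | 0.296 |

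Counting seven p-values gives the same pattern: OSDI 0.020 and 0.024, TBUT 0.102.

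**What baseline does, from printed means only.**
- OSDI before treatment: 79.70 − 74.69 = 5.01 (p=0.197/0.199). After: 37.30 − 27.72 = 9.58. Change: AS 74.69 − 27.72 = 46.97; PFAT+COE 79.70 − 37.30 = 42.40; difference 4.57.
- TBUT, two-eye mean, before: AS (4.38 + 4.44)/2 = 4.41; PFAT+COE (3.83 + 4.11)/2 = 3.97; difference 0.44 s (p=0.121 right, 0.345 left). After: 5.72 v 6.995, difference 1.275 s. Difference in change: 1.275 + 0.44 = 1.715 s.
- Schirmer hardly moves. Right eye: 9.17 post, 9.61 in change. Left eye: 9.28 post, 8.89 in change.

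**Baseline-adjusted OSDI (illustration).** No SDs are legible in the table, so they are back-calculated as SD = difference/(t × √(2/18)) with 34 df and equal arm variances.
- Before: 5.01/(1.316 × 0.3333) = 11.42.
- After: 9.58/(3.088 × 0.3333) = 9.31, or 9.58/(2.931 × 0.3333) = 9.81 if p=0.006.

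For pre-post correlation r, the ANCOVA difference is 9.58 − r × (9.31/11.42) × 5.01. At r=0.5 this is 9.58 − 2.04 = 7.54. Its standard error is 9.31 × √(0.75 × 34/33) × √(2/18 + 5.01²/(34 × 11.42²)) = 2.80, so t = 2.70 and p = 0.011 on 33 df. The largest p over r is 0.0113 (near r=0.43), or 0.0169 if the post p is 0.006. With Schirmer ranked first of four, Holm multiplies by 3: at most 0.034, or 0.051.

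**How far those SDs can be trusted.** The two OSDI p-values could be equal- and unequal-variance versions of one t-test, though the documents do not say so. With equal arms both share one t. Allowing for rounding, p=0.006 then needs about 25 df or fewer. Unequal-variance df = 17(1+k)²/(1+k²), where k is the ratio of arm variances, and 25 df gives k = 0.25. On that reading the arm SDs differ at least about two-fold. For TBUT the same back-calculation gives post SDs of 2.26 (right) and 1.28 (left) after baseline SDs of 1.04 and 1.03, too uneven to support a precise adjusted p-value.

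**The case against.** The best defence is that correction changes little. Schirmer and OSDI survive Holm as printed, only TBUT drops out, and neither document states a superiority conclusion. The 26.5% applies only if no outcome differs, which these results make unlikely. All of that stands. The gap concerns how the results may be read, and a false positive has not been shown.

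A reader might infer that the between-arm method was left open, so that post values, change or adjusted values could be chosen after seeing the data. The SAP table does not support this. It shows post-only comparisons applied uniformly, and baseline is used in the within-arm tests. A post-only t-test is valid, but it discards information already collected.

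A reader might also take the baseline gaps as proof of non-comparable arms. The printed baseline p-values (0.197/0.199 for OSDI, 0.121 and 0.345 for TBUT) are compatible with chance at 18 per arm.

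Finally, one might say that change scores overturn the OSDI result. The 4.57-point difference is plain arithmetic, but its p-value is not in the documents. Under the back-calculated SDs it would be about 0.36, 0.20 or 0.05 at assumed pre-post correlations of 0, 0.5 or 0.8. No between-arm change-score test was planned or reported.

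**Conclusion.** The point holds as an interpretation risk. Four unranked outcomes are tested six times at 5% each, two of them eye by eye, with baseline unused between arms. On the printed p-values, correction removes TBUT and leaves OSDI and Schirmer pointing in opposite directions, so correction alone names no better regimen.

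The baseline effect on the point estimates is certain: 9.58 becomes 4.57 for OSDI in change, and 1.275 becomes 1.715 s for TBUT. The effect on adjusted p-values is not. It depends on back-calculated SDs, equal arm variances and an assumed correlation. Under those assumptions adjusted OSDI stays below 0.05 after Holm if the printed p is 0.004 (worst case 0.034). If it is 0.006, the worst case sits on the threshold (0.051). Whether TBUT remains claimable cannot be settled from the documents.

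**What to change.** Write the following into the SAP before any re-run, and label it post hoc:

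- Use the two-eye mean as the single value per patient for TBUT and Schirmer.
- Make ANCOVA on the baseline value the deciding between-arm analysis for OSDI, TBUT and Schirmer, with a variance estimate that allows unequal arm variances. Keep Mann-Whitney for Oxford.
- Apply Holm across the four outcomes, and report all four with unadjusted p-values beside the adjusted ones.
- Explain the two OSDI p-values at each time point.
- Claim no overall superiority for either regimen while OSDI and Schirmer conflict.
- Reconcile the Protocol's two statements on allocation: one says assignment was random, the next that "the patient chose the treatment". If patients chose, report the OSDI change score as a sensitivity result and state that adjustment does not remove selection bias.

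The cost is a re-run on existing data and a few sentences of text, with no new patients or visits. The drawback is that the method is chosen with the results known, so it carries less weight than a prespecified one. The OSDI difference will shrink (to about 7.5 points at an assumed pre-post correlation of 0.5), and the TBUT claim may be lost.
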